5. ANALYSIS SETS

5.1. SAFETY SET

The Safety Population will include all subjects who receive any amount of study drug (applied at least one patch).

All safety analyses will be based on the Safety Population.

5.2. MODIFIED INTENT-TO-TREAT

The modified intent-to-treat (mITT) population will include all subjects who receive any amount of study drug to treat a qualifying migraine, and who have efficacy data.

All efficacy analyses will be based on the mITT Population.

5.3. PROTOCOL DEVIATIONS

Protocol deviations will be captured during monitoring visits or via remote monitoring. All deviations will be recorded in the Syneos Health clinical trial management system and will be categorized as major or minor. Major protocol deviations will be summarized by deviation type using frequency counts. All deviations will be listed by subject.

6. GENERAL ASPECTS FOR STATISTICAL ANALYSIS

6.1. GENERAL METHODS

The statistical analysis will be conducted following the principles specified in the International Council for Harmonisation (ICH) Topic E9 Statistical Principles for Clinical Trials (CPMP/ICH/363/96).

All statistical tabulations and analyses will be done using SAS®, Version 9.4 or higher.

All results collected in the database will be presented in listings.

Unless otherwise stated, summary statistics including the number of subjects (n), mean, standard deviation (SD), median, minimum and maximum will be presented for continuous variables. Generally, the minimum and maximum values will be presented to the same decimal precision as the raw values, the mean and median values to one more, and the standard deviation, to two more decimal places than the raw values. This decimal place convention may be followed for all data elements. For categorical variables, per category, the absolute counts (n) and percentages (%) of subjects with data, and if appropriate, the number of subjects with missing data, will be presented. Percentages will be presented to one decimal place.

For adverse events, medical history and concomitant medications reported on a per-subject basis, the denominator for the percentage calculation will be the number of subjects at risk in each treatment group. A subject will be considered at risk if the subject is in the analysis set and in the subgroup of interest.

All p-values will be rounded to 4 decimal places. If a p-value is less than 0.0001 it will be displayed as “< 0.0001”.

Due to technical issues with the eDiary, any duplicate eDiary entries for a given time point will utilize the earliest recorded entry for analyses.

Unless otherwise specified all efficacy analyses will be based upon the modified intent-to-treat population and all safety as well as demographic and baseline characteristic analyses will be based upon the safety population.

Only data from nominal protocol scheduled visits will be included in the summary tables. Data from unscheduled visits will not be included in the summary tables but will be included in the listings. Subjects who withdraw/drop out from the study will have their collected ET visit data included in the analysis based on the closest visit window. Visit windows will be assigned by splitting the periods between visits at the midpoint between the visits. If more than one record falls within the window, the one closest to the target date will be used in the analysis.

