2.1 Primary Objective

- To assess the long-term safety of 3.8 mg (administered as two 1.9 mg patches) of M207 for the acute treatment of migraine

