3.2 Selection of Study Population

3.2.1 Number of Subjects

Approximately 400 subjects will be screened to ensure that at least 300 subjects enter the run-in period and that at least 250 subjects are enrolled into the treatment phase. Fifty subjects must complete the entire one-year treatment period and 150 subjects must complete a minimum of six months of treatment.

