6.6. SUBGROUPS

No subgroups analysis will be performed.

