11.2. ADVERSE EVENTS

All systemic and skin AEs, regardless of suspected causal relationship to the investigational products, will be reported. Subject assessed skin adverse events such as skin redness (erythema), skin swelling (edema), skin bruising, skin bleeding, skin itching and skin pain are collected through the eDiary and will also be recorded as adverse events in the eCRF.

All Adverse Events (AEs) will be coded using the Medical Dictionary for Regulatory Activities (MedDRA; version 20.0 or higher). Migraine headaches will not be captured as AEs.

All AEs will be listed by subject. The following listings of AEs will be provided:

- All AEs,
- Study-drug related AEs,
- Serious adverse events (SAEs),
- AEs leading to death, and
- Adverse events leading to study-drug withdrawal.

Only TEAEs will be included in summary tables. An Overview summary table of TEAEs will be produced showing the following categories:

- Any TEAE,
- Study-drug related TEAEs,
- Serious TEAEs,
- TEAEs leading to study-drug withdrawal, and
- TEAEs leading to death.

All TEAEs will be classified by system organ class (SOC) and preferred term (PT). Frequency count and the number of unique subjects of a TEAE will be tabulated by treatment received. For the number of unique subjects reporting, if a subject reported more than one AE that was coded to the same SOC or PT, the subject will be counted only once for that specific SOC or PT.

The following summaries of TEAEs will also be provided:

- TEAEs by SOC and PT,
- Study-drug related TEAEs by SOC and PT,

- Serious TEAEs by SOC and PT,
- TEAEs by maximum severity (mild, moderate, severe or missing) by SOC and PT, and
- TEAEs by strongest causality relationship (not related, possibly related, probably related, definitely related or missing) by SOC and PT.

For TEAEs presented by relationship to study treatment(s), the strongest relationship to study treatment(s) during the study will be presented for each subject if coded to the same SOC or PT. For TEAEs presented by severity, the worst severity during the study will be presented for each subject if coded to the same SOC or PT. TEAEs with missing causality will be counted as related. TEAEs with missing severity will be counted as severe. The same will be true in the individual summaries.

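### Each TEAE is planned as one whole-study crude percentage with no onset-period or exposure-adjusted display, so late-onset events can look rarer than they are, by an amount that depends on attrition

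*SAP*

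**What the plan says.** For adverse events reported per subject, SAP 6.1 states that "the denominator for the percentage calculation will be the number of subjects at risk in each treatment group", and then: "A subject will be considered at risk if the subject is in the analysis set and in the subgroup of interest". SAP 5.1 makes the safety set all subjects with at least one patch applied. SAP 6.6 adds: "No subgroups analysis will be performed". Nothing therefore narrows the denominator by length of follow-up.

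SAP 11.2 gives the counting rule: "Frequency count and the number of unique subjects of a TEAE will be tabulated by treatment received". Within a term, "if a subject reported more than one AE that was coded to the same SOC or PT, the subject will be counted only once". No time interval is attached. In the SAP index, the TEAE tables (14.3.1.1 to 14.3.1.6c) are split by source, relationship, seriousness, special interest and severity. None is split by onset period, person-time or number of applications. Treatment duration and dose counts (SAP 11.1) and subjects present at each visit (SAP 7.1) are summarised separately and are not linked to adverse events.

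Protocol 2.1 gives the primary objective: "To assess the long-term safety of 3.8 mg (administered as two 1.9 mg patches) of M207". Protocol 3.2.1 plans at least 250 subjects in the treatment phase and says: "Fifty subjects must complete the entire one-year treatment period and 150 subjects must complete a minimum of six months of treatment". The synopsis words both completion figures as minima. Protocol 3.2.6.2 replaces treated subjects who leave before six months.

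**The concern.** Protocol 1.3 says that single-attack tolerability was already found acceptable in CP-2016-001 and that this study is to assess repeated use over 6 to 12 months. What the study adds is therefore information by duration.

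A single percentage over everyone ever treated does not provide that. A subject who applied one patch and left remains in the denominator for an event that could only arise in month 10. A replaced early leaver who applied a patch adds to the denominator without adding late follow-up. The result cannot show whether events fade after first use, stay level or emerge late. A reader who takes it as a one-year risk will read late events as rarer than they are among subjects still in the study.

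**Working it through.** **No plan figure to reproduce.** SAP 3.5 says the sample size had no statistical basis, and neither document gives an expected event rate or dropout rate. The check is how far a crude percentage can fall below the risk in subjects followed throughout.

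**Inputs from the documents.** 250 treated; at least 150 completing six months (150/250 = 60%) and at least 50 completing one year (50/250 = 20%). Visit days are 168 and 336 (Protocol Table 10).

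**Assumptions, not in the documents.** Exactly 250 treated; loss linear between Days 0, 168 and 336 and unrelated to the event; true risk 10% over the window in which the event can occur; a second retention case of 200 at Day 168 and 150 at Day 336; and a case with no loss.

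**1. Observed person-time.**
- At the minima: (250+150)/2 × 168 + (150+50)/2 × 168 = 33,600 + 16,800 = 50,400 of 250 × 336 = 84,000 person-days, or 60%.
- At 200/150: 37,800 + 29,400 = 67,200, or 80%.

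**2. Crude percentage.** Let r(t) be the number still followed, s the first day the event can occur and T the window length. The hazard is h = −ln(1 − 0.10)/T. Expected first events = ∫ r(t) · h · exp(−h(t − s)) dt over the window, and the crude percentage is that number divided by 250.

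*Worked case: onset only after Day 168, at the minima.* T = 168 and h = 0.10536/168 = 0.000627 per day. Retention falls from 150 by 100/168 = 0.595 per day. Expected events = 150 × 0.10 − 0.595 × (0.10/h − 168 × 0.90) = 15 − 0.595 × (159.45 − 151.2) = 15 − 4.91 = 10.09. Crude percentage = 10.09/250 = 4.04%.

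**3. What a true 10% shows as.**

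| Retained at Day 168 / Day 336 | Constant hazard over 336 days | Onset only after Day 168 | Onset only after Day 252 |
|---|---|---|---|
| 150 / 50 | 6.1% | 4.0% | 3.0% |
| 200 / 150 | 8.0% | 7.0% | 6.5% |
| 250 / 250 | 10.0% | 10.0% | 10.0% |

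The ratios of shown to true risk barely change for assumed risks from 2% to 20%. For onset after Day 168 at the minima the ratio is 0.40 to 0.41.

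**4. If no late event is seen.** The one-sided 95% upper bound is 1 − 0.05^(1/n): 1.2% for n = 250, 2.0% for n = 150 and 5.8% for n = 50. The reassurance drawn from zero events depends on which n is used.

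**5. Which denominator repairs it.** Splitting by period but dividing by the number present at the start of each period still dilutes. At the minima, retention runs 250, 200, 150, 100, 50 at Days 0, 84, 168, 252, 336. Mean over starting number is 225/250 = 0.90, 175/200 = 0.88, 125/150 = 0.83 and 75/100 = 0.75, so the latest period suffers most. Person-time does not have this fault. In the worked case, 10.09 events over 574 event-free person-months (28-day months) is 1.756 per 100 person-months. Over six months that is a cumulative hazard of 0.105, and 1 − exp(−0.105) returns 10%.

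**The case against.** Crude incidence is a standard safety display. The endpoint in Protocol 7.1.1 and SAP 4.2 is incidence of TEAEs, and the SAP never calls the percentage a 6- or 12-month risk. This stands: as a count of treated subjects with an event, the figure is correct and should stay.

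The completion figures are floors, not forecasts, and with full retention there is no dilution. This also stands.

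The plan does have time-based safety output:
- Investigator bruising, erythema, edema and skin signs, including scarring and pigment change, are tabulated by visit (SAP 11.2.2, Table 14.3.2.3). Under SAP 6.1 the general rule for categorical percentages is subjects with data, so these denominators follow retention.
- eDiary skin reactions are also tabulated per treated migraine (SAP 11.2.1, Table 14.3.2.2).
- In CP-2016-001 at 3.8 mg, general and administration-site disorders affected 45.8% of subjects, against 4.8% for the next largest class listed (Protocol Table 8). The commonest expected reactions are therefore partly covered.

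This narrows the point but does not remove it. The per-migraine tables pool attacks across the whole study. Systemic, serious and withdrawal-leading TEAEs have no display by time, and adverse events of special interest have only a whole-study TEAE table (14.3.1.5). By-subject listings hold the data but are not a prespecified summary for the primary objective. The remark in SAP 15.2.5.2 that denominators need care is generic and defines nothing.

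Finally, the at-risk sentence does not forbid period tables or rates. The defect is that none is planned.

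**Conclusion.** The concern holds as a gap in the planned TEAE displays. The crude percentage is valid, but it is neither a 6-month nor a 12-month risk, and it cannot show when events arise. For events starting after Day 168, the shown-to-true ratio is about 0.40 at the protocol minima, 0.70 with 200/150 retained and 1.00 with no loss. For onset after Day 252 at the minima it is about 0.30. These figures rest on linear loss unrelated to the event, and actual attrition is not given.

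A reader might infer that the plan understates long-term risk as a matter of fact, or that safety is nowhere shown over time. The documents support neither. The first depends on how many subjects leave and on reading the percentage as a fixed-time risk. The second overlooks the by-visit and per-migraine skin tables. The effect is also small for application-site reactions that appear early in most affected subjects. What remains is mainly systemic, serious and withdrawal-leading TEAEs and adverse events of special interest.

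**What to change.** Keep the crude tables and add to SAP 11.2:

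1. TEAEs, serious TEAEs, TEAEs leading to withdrawal and adverse events of special interest by onset period (Days 1-84, 85-168, 169-252, 253 to end). Show the number under observation at the start of each period, and use person-time within the period, or an actuarial or Kaplan-Meier estimate, as the denominator. The start-of-period count alone is not enough.
2. Overall exposure-adjusted rates per 100 person-years and, for TEAEs not already shown per treated migraine, per 100 applications.

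Define person-time as time under adverse event observation from the first application. The treatment duration in SAP 11.1 ends at the last dose and is not the same thing.

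State beside the tables that late-period rates are less precise and come from subjects who remained on treatment. These may be selected, for example by the provision in Protocol 3.2.6.1 that subjects with fewer than 6 qualifying migraines in 12 weeks may be withdrawn.

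The cost is SAP wording and a few extra tables. Onset date and time (Protocol 8.3), eDiary application dates (SAP 11.1) and visit dates are already collected, and study conduct does not change. The downside is wider uncertainty in the late periods, which reflects how much long-term information the study actually holds.

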3.2.6 Early Termination

3.2.6.1 Withdrawal of Subjects

Subjects may be withdrawn from treatment or from the study for the following reasons:

- Subject did not experience at least 6 qualifying migraines within 12 weeks after patch and applicator dispensation (Visit 3);
- At their own request or at the request of their legally authorized representative;
- If, in the investigator's opinion, continuation of treatment would be detrimental to the subject's well-being;
- If the subject experiences any AE believed to be possibly or probably related to study drug and severe enough to warrant withdrawal of treatment;
- If the subject starts and continues to use a prohibited drug, as listed in [Section 6.2.11](#);
- If the subject is non-compliant with the study drug, eDiary completion, or any other requirement of this protocol; or
- If a subject becomes pregnant anytime during the study.

Subjects who early terminate from the study after applying study medication, will return for an early termination visit and a two-week safety follow-up visit if they applied any patches. For all subjects who are withdrawn from study drug or from the study, the reason must be recorded on the appropriate source document and on the appropriate CRF. The subject must be followed up to establish whether the reason was an AE, and, if so, this must be reported in accordance with the procedures in [Section 8.3](#). Subjects with ongoing systemic and skin AEs at study termination will be followed until all significant changes have resolved or become medically stable.

To the extent possible, all examinations scheduled and all data normally collected at completion of the study (the final study visit) must be performed on all subjects who receive study drug but do not complete the study according to protocol. These assessments must be done at the time of the subject's early termination visit.

The investigator must make at least three documented attempts (phone, email, etc.) to contact subjects lost to follow-up until the time of database lock. This includes one certified letter sent to the subject's primary place of residence. A copy must be maintained in the source documentation.

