 - Subject reported skin assessment for bruising, swelling, and/or redness (at 30 minutes, 2 hours, 12 hours, 24 hours and 48 hours post patch administration time points only)
 - Subject reported skin pain and skin itching at 48 hours post patch administration
- Dispense the Subject Skin Grading Card (Appendix 4) with the eDiary and instruct the subject to refer to this card when grading their skin reaction(s)/symptom(s) in the eDiary. The Grading Card will include a subject reminder to contact the study physician if he/she experiences any serious or severe skin reaction(s) at any time point or for worsening or non-resolving reactions at approximately 3 days post patches application (at 72 hours). In addition, the eDiary will remind the subject to call the study physician if he/she experiences any skin reaction(s) and/or symptom(s) at the patch application site which worsens rather than improves over approximately a five-day period. If the subject

contacts the study physician at any time point for worsening or non-resolving reactions, the subject must be seen for an unscheduled visit. The skin reaction(s)/symptom(s) will be assessed, recorded as an adverse event in the eCRF and followed to resolution.

6.1.5 Month 1 (Visit 4), Month 2 (Visit 5), Month 3 (Visit 6), Month 6 (Visit 7)

Visits must be scheduled to occur on (or within ± 7 days) of the protocol specified study day, ie, on study days 28 (Month 1), 56 (Month 2), 84 (Month 3), and 168 (Month 6). The following procedures will be performed at each visit:

- Administer the Migraine Assessment of Current Therapy (Migraine-ACT) which is completed by the subject
- Collect any unused patches, perform accountability, and dispense patches with applicator
- Perform physical exam, (Month 6 only) (height does not need to be recorded)
- Record vital signs: temperature, respiratory rate (RR), blood pressure (BP), and heart rate (HR)
- Collect urine for urine pregnancy test for all WOCBP
- Collect urine for drug abuse testing (Month 6 only)
- Perform 12-lead electrocardiogram (ECG) (Month 6 only)
- Ensure subject is dispensed the Subject Skin Grading Card (to be used with eDiary entries).
- Collect and review subject's eDiary data with the subject for the following:
 - Subject compliance with study drug treatment and subject responses in eDiary

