- Perform Investigator Skin Assessment (presence of blisters, scaly or flakey skin, erosions or open sores, scarring, hyperpigmentation, bruising, redness, and/or swelling) of upper arm where patches have been applied
- Any cutaneous signs or symptoms found on the investigator skin assessment will be recorded as an adverse event on the eCRF and followed to resolution.
- Record concomitant medications
- Record adverse events. In addition, any skin reaction(s) entered into the eDiary by the subject must also be recorded as an adverse event in the eCRF and followed to resolution.

6.1.6 Month 9 (Visit 8) and Month 12 End of Study Final Visit (Visit 9/or Early Termination)

The Month 9 and 12 visits are to be scheduled on (or within ± 7 days) of the protocol specified study day, i.e., on study days 252 (Month 9) and 336 (Month 12). The following procedures will be performed. If a subject terminates early from the study at any time after applying M207, an Early Termination visit must be scheduled to occur within 7-14 days after the subject's last patch application.

- Administer the Migraine Assessment of Current Therapy (Migraine-ACT) to be completed by the subject
- Collect the applicator, any unused patches, and perform accountability
- Dispense M207 patches (Month 9 only)
- Perform physical exam, including weight and height (Month 12 final visit/or early termination only)
- Record vital signs: temperature, respiratory rate (RR), blood pressure (BP), and heart rate (HR)
- Collect blood (4-hr fasting) for clinical laboratory measurements including clinical chemistries and hematology (Month 12 final visit/or early termination only)
- Collect urine for urine pregnancy test for all WOCBP
- Perform 12-lead electrocardiogram (ECG) (Month 12 final visit/or early termination only)
- Ensure subject is dispensed a Subject Skin Grading Card (at Month 9 only)
- Collect and review subject's eDiary data with the subject for the following:
 - Subject compliance with study drug treatment and subject responses in eDiary
- Perform Investigator Skin Assessment (presence of blisters, scaly or flakey skin, erosions or open sores, scarring, hyperpigmentation, bruising, redness, and/or swelling) of upper arm where patches have been applied
- Any cutaneous signs or symptoms found on the investigator skin assessment will be recorded as an adverse event on the eCRF and followed to resolution.
- Record concomitant medications

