3.4. SUBJECT SELECTION

Approximately 400 subjects will be screened to ensure that at least 300 subjects enter the run-in period and that at least 250 subjects are enrolled into the treatment phase. Fifty subjects must complete the entire one-year treatment period and 150 subjects must complete a minimum of six months of treatment.

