6.4. VISIT WINDOWS

Nominal Visits will be used in the analyses as reported on the eCRF. As per section 6.1, the subjects who withdraw/drop out from the study will have their ET visit data collected included in the analysis based on the closest visit window.

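### The closest-to-target rule drops an estimated 41–46% of early-termination investigator skin ratings from the by-visit skin table (Table 14.3.2.3)

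*SAP*

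**What the plan says.** SAP 6.1 sets three rules that work together. ET data are windowed: "Subjects who withdraw/drop out from the study will have their collected ET visit data included in the analysis based on the closest visit window". The cuts are fixed: "Visit windows will be assigned by splitting the periods between visits at the midpoint between the visits". Ties are resolved by distance: "If more than one record falls within the window, the one closest to the target date will be used in the analysis". SAP 6.4 uses nominal visits as reported on the eCRF and repeats that leavers "will have their ET visit data collected included in the analysis based on the closest visit window". SAP 6.1 also keeps unscheduled visits out of the summary tables.

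Investigator skin assessments start at Month 1 and are made at every clinic visit, including ET (Protocol Table 10, 6.1.5, 6.1.6). SAP 4.2 and 11.2.2 summarise them at Months 1, 2, 3, 6, 9 and 12 and at the two-week post-study visit; the index has one table for this, 14.3.2.3. No ET, last-value or worst-value row is described for it. By contrast, SAP 11.2.1 tabulates the subject-reported eDiary skin data at each subject's worst grade at any time.

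**The concern.** When a subject attends a scheduled visit and then leaves before the next midpoint, both records sit in one window and only one is used. The scheduled visit was aimed at the target day and the ET visit was not, so the ET record usually loses. Take a subject seen on Day 84 who terminates on Day 110. The Month 3 window runs to Day 126. The distances from target are 0 and 26 days, so the Day 84 rating is kept and the Day 110 rating is not tabulated. Had the same subject left on Day 130, the record would have entered the Month 6 row. Whether a leaver's ET rating is tabulated therefore depends on the calendar, not on the finding.

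The primary objective is long-term safety of a patch applied repeatedly to the upper arm, so how the skin looked when subjects stopped is a result readers will want from the by-visit table. Unscheduled visits add to the gap. Protocol 6.1.4 and 6.2.13 require one when a subject contacts the physician about a worsening or non-resolving reaction. A subject seen that way who then leaves can have both examinations absent from the table.

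**Working it through.** The plan gives no figure for displaced ET records, so there is none to reproduce. The rule can be applied directly.

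**Inputs**
- Target days 28, 56, 84, 168, 252 and 336, each ±7 days (Protocol 6.1.5, 6.1.6, Table 10).
- Midpoints: (28+56)/2 = 42, (56+84)/2 = 70, (84+168)/2 = 126, (168+252)/2 = 210, (252+336)/2 = 294.
- Departure times: not given. Base assumption: uniform over Days 1 to 336, a span of 335 days.

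**Visits on target.** An ET skin record is displaced if it falls between a target day and the next midpoint:
- 14 + 14 + 42 + 42 + 42 = 154 days; 154/335 = 46.0%.
- Before Day 168: 14 + 14 + 42 = 70 days; 70/167 = 41.9%.
- From Day 168: 84/168 = 50.0%.

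**Visits spread evenly over ±7 days.** An ET record d days after target (0 < d < 7) loses with probability d/7, and always loses from d = 7 to the midpoint. Each of the five windows therefore gives back 7 − 3.5 = 3.5 days:
- 154 − 5 × 3.5 = 136.5; 136.5/335 = 40.7%.
- Before Day 168: (70 − 3 × 3.5)/167 = 59.5/167 = 35.6%.
- From Day 168: (84 − 2 × 3.5)/168 = 77/168 = 45.8%.
- In a further 17.5/335 = 5.2% the ET record replaces the scheduled one.

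A simulation with whole-day visits and at least one day between visit and ET gives 40% and 5%.

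**Other departure patterns (simulated)**

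| Pattern | On target | ±7 days |
|---|---|---|
| Exponential, 20% to 80% leaving by Day 336 | 46–47% | 38–40% |
| 30% of ET visits on Days 85–105, rest uniform | 62% | 53% |

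The second row is illustrative. It is prompted by the withdrawal reason in Protocol 3.2.6.1 of fewer than six qualifying migraines in the 12 weeks after dispensation.

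**First two weeks.** If all assessments share one set of windows, Day 1 has a window ending at (1+28)/2 = 14.5. An ET visit before then maps to Day 1, which has no planned skin row. This is not displacement, because no Day 1 skin record exists, but the record has no place in the table. Under uniform departures it is a further 13.5/335 = 4.0%.

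**Counts.** SAP 3.4 requires at least 250 subjects in the treatment phase and states: "Fifty subjects must complete the entire one-year treatment period and 150 subjects must complete a minimum of six months of treatment". At those floors, 250 − 150 = 100 could leave before six months and 250 − 50 = 200 before one year. With 100 departures in each half and every leaver attending ET:
- ±7 days: 100 × 0.356 + 100 × 0.458 = about 81 of 200 displaced.
- On target: 100 × 0.419 + 100 × 0.500 = about 92 of 200.

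These are upper-end counts, not forecasts.

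**Other assessments**
- Laboratory tests: none displaced. They are taken only at screening and Month 12/ET, so an ET result has no competing on-treatment record (reading the shift as baseline to any post-baseline value).
- ECG and physical examination: 42/335 = 12.5% with common windows, or 84/335 = 25.1% with windows on their own Month 6 and 12 schedule. The index has them only as listings.
- Migraine-ACT: same visits as skin, so the same shares. SAP 8.1.8 plans frequencies by visit, though the index has only a listing.

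**The case against.** A reader might infer that nearly half of all ET assessments vanish, that the last examination of leavers is missing from the safety tables, and that what is displaced survives only in listings. The documents do not support this.
- Any skin sign found by the investigator, including at ET, must be recorded as an adverse event (Protocol 6.1.6, Appendix 6). The TEAE tables have no visit windows. A subject who stops for a skin reaction appears there, and among TEAEs leading to withdrawal.
- The ET visit is followed 14 to 28 days later by Visit 10, with its own skin assessment (Protocol 6.1.8), summarised separately. If attended, that is the last skin examination, and it is tabulated.
- The eDiary skin tables are by time after patch or by worst grade, so visit windows do not touch them. Vital signs are indexed only as listings.

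All of this stands, and it confines the point. It does not replace the lost rating. ET is scheduled 7 to 14 days after the last patch, so Visit 10 falls 21 to 42 days after it, when a transient reaction may have faded. AE severity follows Protocol 8.2.1.3, which is a different scale from the 0–3 extent rating, and AE tables give no by-visit prevalence.

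A reader might also infer that the table is biased towards subjects doing well. That is plausible, not shown. A displaced subject stays in the table through the scheduled record. The first withdrawal reason listed is too few migraines, not tolerability. And 7 to 14 days after the last patch, the ET rating may itself be the milder one.

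**Conclusion.** The point holds for the by-visit investigator skin table and for any by-visit Migraine-ACT summary. Under uniform departures, about 41% (visits spread over ±7 days) to 46% (visits on target) of ET skin assessments are displaced; for departures before Day 168 the range is about 36% to 42%. Across the other patterns tried it is roughly 38% to 62%. These shares rest on assumed departure times, attendance at the preceding scheduled visit, and one set of midpoint windows for the skin schedule.

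It is a gap in how one descriptive table presents data already in hand. It does not undermine the adverse event or laboratory results. It is worth fixing because this table is the only by-visit clinic safety table in a long-term patch-safety study, and the displaced ratings all come from subjects who left.

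**What to change.** Amend SAP 6.1 and 6.4 so that scheduled visits keep their own rows and ET records do not compete with them. Add two rows to Table 14.3.2.3:
- Early termination / last on-treatment assessment.
- Worst post-baseline assessment, with ET and unscheduled examinations included. This matches the worst-grade approach SAP 11.2.1 already takes for eDiary skin data.

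Treat ET the same way in any by-visit Migraine-ACT or vital-sign summary. State whether windows are common or set per assessment, which also settles where an ET visit in the first two weeks belongs.

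The cost is SAP wording and two table rows; no new data or visits are needed. Summary rates may look slightly worse.
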